2.0 Objectives*

2.1 Primary Objectives:

1. Measure physical activity and sleep for up to 365 (\pm 30 days) days using a Garmin physical activity tracker among youth and young adults with T1D.
2. Evaluate the impact of physical activity and sleep related variables on rate of DKA admission over 90 and 180, and 365 \pm 30 days
3. Evaluate the impact of physical activity and sleep related variables on change in Time in Range and other continuous glucose monitor-derived metrics of glycemic control over 90, 180, and 365 \pm 30 days
4. Test the impact of physical activity and sleep related variables on machine learning models to predict change in HbA1c, DKA admissions, and change in Time in Range over 90, 180 and 365 \pm 30 days

2.2 Secondary Objectives:

1. Examine for correlations between self-reported physical activity (IPAQ), hypoglycemia fear (HFS-II), and parent hypoglycemia fear (HFS-P) at 0, 6, and 12 months after study enrollment.
2. Evaluate any change in physical activity levels via self-report with the IPAQ survey (to allow comparisons to external cohorts).
3. Evaluate any change in how participants feel about episodes of hypoglycemia while wearing the Garmin physical activity tracker via the Hypoglycemic Fear Scale II (HFS-II)
4. Evaluate any change in how parents feel about episodes of hypoglycemia in their children wearing the Garmin physical activity tracker via the Hypoglycemic Fear Scale II for Parents (HFS-P)

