4.0 Study Endpoints

1. Minutes/day of Moderate-to-vigorous physical activity (MVPA) – from Garmin device over 30, 90, 180, and 365 ± 30 days
2. Sleep minutes/day – derived from Garmin device over 30, 90, 180, and 365 ± 30 days
3. Other activity metrics derived from Garmin device over 30, 90, 180, and 365 ± 30 days
4. HbA1c – collected from Electronic Medical Record, obtained via standard care (binned as 46-135 days, 136-225 days, 226-305 days, and 306-410 days)
5. Hospital admissions for DKA (0-180 days and $181-365 \pm 30$ days)
6. 14-day Time in Range and other CGM-derived metrics of the quality of glycemic control over 30, 90, 180, and 365 ± 30 days
7. Model performance characteristics (e.g. precision, recall, F1) of predictive models for the outcomes listed in 4.1-4.6

5.0 Study Design*Participants with T1D treated at the Children's Mercy Endocrine clinic aged 8-21 years old will be asked to wear a Garmin VivoSmart 4 (or later) physical activity tracker for at least 6 months. This tracker will collect detailed physical activity and sleep data as measured by moderate to vigorous physical activity (MVPA) and sleep minutes/day. The tracker collects heart rate and accelerometry data, collected into the Garmin Connect application. The diabetes center will use the Garmin Health API connection developed by Children's Mercy Research Informatics to extract the data into a data warehouse in Microsoft Azure (CMH account). As noted in previous studies, MVPA is automatically measured by the tracker when the wearer runs for >1 minute or walks for >10 consecutive minutes. The weekly MVPA and step count are both weighted by multiplying the mean of weekday activity by 5, adding it to the mean of weekend activity and dividing the sum by 7.

$$\text{Weighted MVPA} = \frac{[(\text{MVPA}) \times 5] + (\text{MWVPA})}{7}$$

$$\text{Weighted step count} = \frac{[(\text{MSC}) \times 5] + (\text{MSC weekend})}{7}$$

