7.2 Exclusion Criteria

- Participants who do not meet age criteria above
- Participants who do not have T1D
- Participants who are unwilling to wear the device for at least 6 months

7.3 Equitable Selection:

Participants will be accrued to the study from the patient population at Children's Mercy. No participant will be excluded based on sex, race, or ethnicity. However, if a non-English speaking participant speaks a language not supported by the Garmin device, they will not be able to participate.

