9.2 Pre-Screening prior to HIPAA Authorization

Will any of the identification methods checked above involve access to Protected Health Information (PHI) prior to obtaining HIPAA Authorization?

- Yes

SHORT TITLE:

No

- *If yes, a “Partial Waiver of HIPAA Authorization” is required. Be sure to make this selection in the “HIPAA & Confidentiality” section below and complete [Addendum E: Waiver/Alteration of HIPAA Authorization](#)*

9.3 Recruitment of Potential Participants:

Participants will be recruited from the CMH diabetes clinic, at diabetes events CM participates in (such as T1D walks or camps), by identifying youth 8-21 Y.O. with T1D who have a predicted rise in HbA1c of 0.3 points, by CM approved electronic communication (emails or texts- including the Health Device Portal Messaging) or by physician referral to the study. Flyers describing the study generally (discussing who researchers are looking for, what they would have to do, and receiving the Garmin devices) will be posted in the diabetes clinic, CM study lists (I.e. Find a Study, the clinic intake form), and at T1D events. Also, the flyer/ link to the flyer can be sent to T1D patients via email (via CM approved email servers)/ text (CM approved SMS servers including the Health Device portal messaging). The flyers will contain the study coordinator and PI contact information so the participant can reach out for information/ screening. After the initial screening to confirm eligibility, participants will be contacted via telephone and asked if they want to be emailed the consent letter to obtain verbal consent. Participants will be called up to three times, and all visits will be virtual unless a participant requests to be in person, if so the study visit will be coordinated with their standard of care clinical visit.

10.0 Surveys and Psychometric Testing:

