16.0 Potential Benefits*

There may not be direct benefits from taking part in the research. However, as the participants with T1D react to the watch interventions, they may become more active and more aware of stress throughout the day. As these elements improve, participants may see improvement in self-care, diabetes management, HbA1c, and decreased potential for long-term diabetes complications. There is no direct benefit for the parents of participants with T1D. The knowledge gained from this study may help other healthcare providers know how to better serve their patients by utilizing Garmin trackers or similar products to promote activity.

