28.0 Statistical Analysis*

28.1 Matched Cohort:

Where possible, the intervention group will be compared to a matched cohort identified using propensity score matching. The propensity score for the groups will take into consideration age, baseline HbA1c, duration of diabetes, insurance, race, device usage, and time in range.

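### The propensity score omits the HbA1c forecast used to recruit some participants, so a matched comparison of HbA1c or time in range could be unbalanced on expected trajectory

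*Combined protocol and SAP*

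**What the plan says.** Section 28.1 (Matched Cohort) reads: "Where possible, the intervention group will be compared to a matched cohort identified using propensity score matching". It continues: "The propensity score for the groups will take into consideration age, baseline HbA1c, duration of diabetes, insurance, race, device usage, and time in range". That is a list of seven covariates. It contains neither a forecast of HbA1c nor recruitment route, and Section 28.1 names no outcome for the comparison.

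Section 9.3 gives, as one of several recruitment routes, "by identifying youth 8-21 Y.O. with T1D who have a predicted rise in HbA1c of 0.3 points". Other routes need no forecast: the clinic, physician referral, flyers, electronic messages, and recruitment "at diabetes events CM participates in (such as T1D walks or camps"). Section 7.1 does not make a predicted rise an inclusion criterion. Section 7.2 excludes "Participants who are unwilling to wear the device for at least 6 months".

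HbA1c is an endpoint (Section 4.0, item 4), "collected from Electronic Medical Record, obtained via standard care". Time in range is item 6 of the same list. Section 16.0 states that "participants may see improvement in self-care, diabetes management, HbA1c, and decreased potential for long-term diabetes complications".

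**The concern.** A propensity score should include variables that influence both who enters the treated group and the outcome. Here a forecast of HbA1c change brings some youth into the tracker group, and by definition it predicts HbA1c change. Matching on current HbA1c and time in range equalises level but not expected direction: two youths with the same values today can have different forecasts.

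If the matched contrast is run on change in HbA1c or time in range, and controls are drawn without regard to the forecast, part of the difference could be a trajectory that was expected before any tracker was worn. Taken alone, this component makes the tracker group look worse, so it would tend to hide a benefit or suggest harm.

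**Working it through.** **No stated figure to reproduce.** The documents give no alpha, power, effect size or SD for the matched comparison. They also do not give the share recruited on the forecast, the accuracy of the forecast, or its inputs.

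**Text check.** Comparing the recruitment routes in Section 9.3 with the covariates in Section 28.1 shows that the forecast is in the first and absent from the second.

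**Illustration 1: bias and rejection rate.** From the documents: a rise of 0.3 points (Section 9.3) and up to 200 youth (Section 1). Assumed: 200 matched controls, SD of HbA1c change 1.0 to 1.5, a two-sided 5% test, and no true tracker effect.

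- Bias = (pT − pC) × m × k. Here pT and pC are the shares of participants and matched controls with a predicted rise, whatever their entry route. The mean predicted rise is m. The part of the forecast that is realised and not captured by the listed covariates is k.
- SE = SD × √(2/n), ignoring within-pair correlation. For n = 200 this is 0.10 (SD 1.0) or 0.15 (SD 1.5).
- Rejection rate = P(|Z + bias/SE| > 1.96).

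| pT − pC | m | k | n per group | Bias (points) | Rejection, SD 1.0 | Rejection, SD 1.5 |
|---|---|---|---|---|---|---|
| 0.10 | 0.3 | 0.5 | 200 | 0.015 | 5.3% | 5.1% |
| 0.10 | 0.3 | 1 | 200 | 0.030 | 6.0% | 5.5% |
| 0.25 | 0.3 | 0.5 | 200 | 0.0375 | 6.6% | 5.7% |
| 0.25 | 0.3 | 1 | 200 | 0.075 | 11.7% | 7.9% |
| 0.50 | 0.3 | 0.5 | 200 | 0.075 | 11.7% | 7.9% |
| 0.50 | 0.3 | 1 | 200 | 0.15 | 32.3% | 17.0% |
| 0.25 | 0.3 | 0.5 | 100 | 0.0375 | 5.8% | 5.4% |
| 0.50 | 0.3 | 1 | 100 | 0.15 | 18.6% | 10.9% |
| 0.25 | 0.5 | 0.5 | 200 | 0.0625 | 9.6% | 7.0% |

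The last row is included because Section 9.3 does not say whether 0.3 is a minimum. If it is, the mean rise among those selected would exceed 0.3; 0.5 is an assumption.

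**Illustration 2: how much the listed covariates might remove.** This simulation assumes that predicted change is normal with mean 0 and SD 0.3 to 0.5. A share of 25% to 50% of enrollees is selected with a forecast of at least 0.3, and the rest are drawn at random. Controls are matched on covariates that explain a fraction R² of the forecast. The remaining gap in predicted change is:

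- R² = 0: about 0.12 to 0.30 points
- R² = 0.5: about 0.06 to 0.15 points
- R² = 0.9: about 0.01 to 0.03 points

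If the listed covariates largely determine the forecast, little imbalance remains. If they do not, the gap can be material.

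**The case against.** The strongest case on the other side has four parts.

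1. **The affected analysis is inferred.** Section 28.1 names no outcome and makes the comparison conditional. No objective in Section 2.0 is a tracker-versus-control contrast. HbA1c change appears there only as a target of "machine learning models to predict change in HbA1c, DKA admissions, and change in Time in Range". The link to HbA1c rests on the endpoint list and on a hedged benefits paragraph. This stands, and it limits the importance of the point.

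2. **The listed covariates may already do much of the work.** Current HbA1c, time in range, age and diabetes duration are natural inputs to an HbA1c forecast. This also stands. However, the model is not described, so full capture cannot be assumed.

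3. **The size is assumed throughout.** The largest figures need a 50-percentage-point difference in shares, a fully realised forecast, and seven covariates that capture none of it. The forecast is only one route among several, and controls from the same clinic will include predicted risers too. This stands: several plausible cases remain close to 5%.

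4. **How controls are sampled is not stated.** They might already be chosen on the forecast. The text available for this review ends with Section 28.1, so the point rests on the covariate list as written. If controls are so chosen, one sentence in Section 28.1 settles the matter.

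A reader might go further and infer that the whole cohort was selected for worsening control, that the matched comparison is invalid, or that the study's main objectives are compromised. The documents do not support this. The forecast is not an eligibility criterion, its share of enrolment is unknown, and the objectives in Section 2.0 are analysed within the cohort. Nor can the net direction of bias be stated: other routes attract volunteers, and youth unwilling to wear the device for 6 months are excluded.

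**Conclusion.** The gap is real but of limited importance. A variable that drives entry for some participants and predicts HbA1c change is missing from the listed propensity covariates. Imbalance in expected trajectory follows only if three conditions hold: the matched comparison is used for change in HbA1c or time in range, controls are not selected on the same forecast, and the listed covariates do not already capture it.

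The documents do not allow the size to be derived. On the assumptions shown, with 200 per group and m = 0.3, the bias ranges from 0.015 to 0.15 points and the rejection rate under no effect from about 5% to 32%. Only the larger imbalances matter. This component alone would count against the tracker. The point supports a low-priority improvement, not a claim that the comparison is wrong.

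**What to change.** In Section 28.1:

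1. Add the pre-enrolment predicted HbA1c change to the propensity score, computed with the same model at the index date for controls. Alternatively, draw controls for predicted-rise entrants from patients who meet the same predicted-rise criterion. Report balance on predicted change after matching.
2. Record each participant's recruitment route at entry. Report a sensitivity analysis that excludes predicted-rise entrants and their matched controls.

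The cost is a few lines of analysis wording, one added covariate and one recorded field. There are three downsides: the forecast must be run for candidate controls, which the documents do not show to be feasible; some participants may lose a close match; and the sensitivity analysis will be less precise because it is smaller.

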26.0 Data Collection*

This study will be completely integrated into the Diabetes Data Dock at CMKC. Data will be collected and paired with the other wearable devices, such as pump and continuous glucose monitor readings.

SHORT TITLE:

Surveys (IPAQ, HFS-II/P) will be collected at baseline and EOS. Data collected from EMR will include medical history, lab results, demographics, clinical data, insurance type (public vs private).

Child/ adult participant data -

Demographic data: We will use the REDCap demographics survey to collect demographic data. We may use the Diabetes Data Dock and/or the child's electronic health record to verify or extend demographic data (e.g., T1D diagnosis, history of T1D-related complications, T1D regimen, shipping address to send the Garmin Device, shipping history).

HbA1c data: We will use routine T1D care POC HbA1c levels to at baseline and at post-treatment (~3 months post baseline).

CGM or SMBG data: Families will use their personal, prescribed CGM or standard blood glucose monitor (SMBG) throughout the study. Families will share CGM data with the study team using their personal, CM connected account. Data will be download automatically to the Diabetes Data Dock using API.

Insulin delivery data: Participants will use their personal, prescribed insulin delivery device throughout the study. Participants and parents/LARs of adolescents will share participants' insulin device data with the study team using their personal, CM connected account.

Questionnaire data: We will use REDCap to electronically collect any survey data, including participants' daily activity schedules. We will use a single REDCap database for all study participants. This REDCap data base will reside on a CM secured server.

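### The 28.1 propensity score omits prior DKA admission, clinic attendance and sex, so residual confounding of uncertain direction is likely if DKA, HbA1c or TIR is compared with the matched cohort

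*Combined protocol and SAP*

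**What the plan says.** Section 28.1 plans a matched comparison: "Where possible, the intervention group will be compared to a matched cohort identified using propensity score matching". The score is then specified: "The propensity score for the groups will take into consideration age, baseline HbA1c, duration of diabetes, insurance, race, device usage, and time in range". That is seven variables. DKA history, any direct measure of contact with the clinic, and sex are not among them. The section does not say which outcomes the comparison covers.

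DKA admission appears in two places. Primary objective 2 (section 2.1) is to "Evaluate the impact of physical activity and sleep related variables on rate of DKA admission over 90 and 180, and 365" days (± 30). In section 4.0, endpoint 5 begins "Hospital admissions for DKA (0-180 days and" and adds a second window running to 365 ± 30 days. Section 4.0 does not rank its endpoints.

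Two provisions shape who enters the tracker group. Section 7.2 excludes "Participants who are unwilling to wear the device for at least 6 months". Section 9.3 lists several recruitment routes, among them physician referral and the identification of "youth 8-21 Y.O. with T1D who have a predicted rise in HbA1c of 0.3 points".

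On data, section 26.0 takes clinical data, laboratory results and demographics from the medical record. It allows the record or the Diabetes Data Dock to be used for participants' "history of T1D-related complications".

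**The concern.** For an event that can recur in the same patient, the patient's own history of that event is a basic matching variable. The plan follows DKA admissions but does not match on them.

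Entry to the tracker group is also selective. Families must be reached, ask for the information letter and call back (21.0). They must also accept a device that is to be worn daily and charged as often as every 2 to 3 days (15.0). No parallel filter is stated for the comparators. Attendance and DKA history are plausible markers of who gets through these steps, and plausible predictors of later DKA, HbA1c and time in range.

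The comparison invites a causal reading. Section 28.1 calls the tracker users an intervention group, 6.2 describes a behavioural intervention, and 16.0 anticipates better diabetes management and HbA1c. If the groups differ on DKA history or engagement after matching, that difference would be mixed into whatever is attributed to the tracker.

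**Working it through.** **1. The covariate list against the outcomes.** Baseline HbA1c and time in range are both in the score, so the glycaemic outcomes have a baseline counterpart. DKA admission has none. HbA1c and time in range describe glucose level, and neither records an admission. Device usage is undefined. If it means CGM or pump use, it captures part of engagement but not visit attendance.

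**2. Selection into the tracker group.** The willingness criterion (7.2) and the call-back step (21.0) would tend to admit more engaged families, which favours the tracker group. The predicted-rise route and physician referral (9.3) could bring in youth at higher risk, which works against it. A predicted rise is not the same as a high baseline value, so matching on baseline HbA1c does not remove that route's effect. The documents do not say how many participants come by each route, so the net direction cannot be settled.

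**3. Size.** The documents give no DKA rate, prior-DKA prevalence, matching ratio or comparator number. There is no plan figure to reproduce and no estimate can be made. What follows only shows what an imbalance would do. All inputs except the 200 enrolled youth (section 8.0) are assumptions.

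Let p1 and p0 be the proportions with prior DKA in the tracker and matched groups after matching, and k the risk ratio for DKA given prior DKA. With no tracker effect, the expected risk ratio is

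(1 + p1(k − 1)) / (1 + p0(k − 1)).

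| Prevalences | k | Tracker group has the lower | Tracker group has the higher |
|---|---|---|---|
| 5% and 10% | 2 | 1.05/1.10 = 0.95 | 1.10/1.05 = 1.05 |
| 5% and 10% | 5 | 1.20/1.40 = 0.86 | 1.40/1.20 = 1.17 |
| 5% and 10% | 10 | 1.45/1.90 = 0.76 | 1.90/1.45 = 1.31 |
| 5% and 15% | 2 | 1.05/1.15 = 0.91 | 1.15/1.05 = 1.10 |
| 5% and 15% | 5 | 1.20/1.60 = 0.75 | 1.60/1.20 = 1.33 |
| 5% and 15% | 10 | 1.45/2.35 = 0.62 | 2.35/1.45 = 1.62 |

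With equal prevalences the ratio is 1.00 for every k.

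**4. In events.** Assume 200 per group (1:1 matching) and an annual DKA risk of 2% in youth without prior DKA. For 5% against 10% and k = 5, the expected numbers with an event are 200 × 0.02 × 1.20 = 4.8 and 200 × 0.02 × 1.40 = 5.6. At a 5% base risk they are 12.0 and 14.0. A two-proportion power calculation puts the chance of a result at two-sided 0.05 in the direction of the imbalance at 0.044 and 0.060, against 0.025 with no imbalance. In the most extreme row (5% against 15%, k = 10) the counts are 5.8 and 9.4, or 14.5 and 23.5, and the chances are 0.154 and 0.335.

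**The case against.** The strongest reply is that the link to DKA is inferred. Section 28.1 names no outcome and plans the comparison only where possible. Primary objective 2 asks how activity and sleep variables relate to DKA. Those variables come from the tracker, which nothing shows the comparators would have, so a comparison of tracker users with matched patients does not answer that objective. This stands. The point is therefore conditional on the comparison being used for DKA, HbA1c or time in range, and DKA should not be called the primary outcome of the matched analysis.

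Second, the score already carries some information on engagement, through device usage, HbA1c and time in range. Matching on time in range also presumes available CGM data, which may remove some disengaged comparators. This stands too. The fair description is residual confounding, and the balance actually achieved is unknown.

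Third, the supplied text ends at 28.1, so silence about how the cohort is assembled proves little. That is correct, but the point rests on a list that is present. Nothing in its wording signals that further variables will be added.

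A reader might infer that selection must flatter the tracker and that a spurious reduction in DKA is to be expected. The documents do not support that, because the two routes in 9.3 could reverse the sign. A reader might also want the comparators limited to patients never approached. Flyers, emails, texts and the clinic intake form (9.3, 24.1) make approach hard to define, and those untouched by such outreach may be disproportionately non-attenders. That restriction could worsen the imbalance it was meant to cure.

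**Conclusion.** The point holds in conditional form. The score omits prior DKA admission, clinic attendance and sex, although DKA is a stated endpoint under a primary objective and entry to the tracker group is selective. If the matched comparison is used for DKA, HbA1c or time in range, residual confounding by DKA history and engagement is likely. Neither its sign nor its size can be read from the documents. The assumed ranges give a null risk ratio for DKA anywhere from 0.62 to 1.62. At 5% against 10% and a 2% base risk, with k = 5, the gap is under one event per 200. The illustration does not extend to HbA1c or time in range. The change is worth making before outcomes are compared, since choosing covariates afterwards would be harder to defend.

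**What to change.** In 28.1, add three variables to the propensity score, taken from the medical record for both groups:

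- any DKA admission in the 12 months before the index date;
- diabetes clinic visits attended in those 12 months;
- sex.

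Report standardized differences on all three after matching. Add a sentence stating that willingness to wear the device cannot be matched, so the comparison is not by itself evidence of a tracker effect.

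The cost is small. Matching on HbA1c, time in range and insurance already needs comparator records, so this should be an extension of the same query. The access under which comparator data are drawn must cover the added items, because section 26.0 describes complication history for participants only. The index date for comparators has to be defined. Section 7.1 admits youth diagnosed more than 6 months ago, so the text should also say how an admission at diagnosis within the look-back is counted. Matching becomes slightly harder, and a few participants may go unmatched.

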If the subject wears the tracker for >8 hours between 9 AM and 9 PM, the day is used in the weighing calculation (Grimes et al., 2022). Clinical data will be collected from the medical record and coded (labeled with the study ID to minimize use of personal data). Also, self-reported personal health will be collected from the CMH-approved vendor software to which they upload their self-management device data. Baseline and end of study surveys including International Physical Activity Questionnaire (IPAQ), the Hypoglycemic Fear Scale II (HFS-II) for participants, and Hypoglycemic Fear Scale for parents (HFS-P) will be collected from participants/ parents. Surveys will be given to participants based on their ages and the ages surveys are validated for.

Table of Events:

	Pre-screening (Pre-consent)	Visit 1 Day 1 app x.	Visit 2 ^a Day 14 appx. (PRN)	Visit 3 ^a Day 28 appx. (PRN)	Visit 4 ^a Day 56 appx. (PRN)	Visit 5 Day 180 appx.	Visit 6 Day 365 appx.	Unscheduled Visit
EMR Review Eligibility	X							
Verbal Consent		X						
Demographics		X						
Clinical history ^b		X					X	
Send Garmin tracker		X						
Surveys ^c		X				X	X	
Mid-Study Check-In Survey						X		
Garmin Troubleshooting Visits			X	X	X			

- a. Additional virtual or in person visits may be scheduled at Visit 2, Visit 3, and Visit 4 as needed for device troubleshooting and additional education, depending on the needs of the subjects
- b. A1c will be drawn SOC as a part of the clinical history, in the absence of A1c results, GMI will be deduced from CGM data
- c. The IPAQ (for >15 YO) and HFS-P/HFS-II (HFS-II child for 11-18 Y.O., HFS-II adult for >18 YO)

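### Section 28.1 gives no number of readings and no pre-enrolment window for HbA1c or time in range in the propensity score, so if the groups' usual levels differ, regression to the mean may leave a false difference.

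*Combined protocol and SAP*

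**What the plan says.** Section 28.1 states: "Where possible, the intervention group will be compared to a matched cohort identified using propensity score matching". The score uses "age, baseline HbA1c, duration of diabetes, insurance, race, device usage, and time in range". HbA1c and TIR are its only direct measures of glycaemic level. Neither has a window or a number of readings, and no index date is given for controls.

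Other sections do not fill the gap:

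- **HbA1c source.** Section 26.0 says "We will use routine T1D care POC HbA1c levels to at baseline and at post-treatment (~3 months post baseline"). It mentions no averaging of earlier values. The HbA1c bins in Section 4.0 start at day 46, so no baseline window is listed.
- **HbA1c substitute.** Footnote b to the Table of Events (Section 5.0) says "in the absence of A1c results, GMI will be deduced from CGM data". The baseline value could therefore come from two different measures.
- **TIR.** Section 4.0, item 6, lists "14-day Time in Range and other CGM-derived metrics of the quality of glycemic control over 30, 90, 180, and 365" days as an endpoint. No pre-enrolment TIR is defined. Section 26.0 also allows participants who use a standard glucose meter (SMBG) rather than CGM.
- **Recruitment.** One route in Section 9.3 is "by identifying youth 8-21 Y.O. with T1D who have a predicted rise in HbA1c of 0.3 points"; physician referral is another. Section 7.2 excludes youth who would not wear the device for 6 months. None of these features is in the score.

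**The concern.** One HbA1c, or a short TIR window, is a noisy reading of a person's usual level. Suppose tracker users come from a population with a higher usual level than the control pool. Matching on the noisy reading then tends to pair a participant who is usually high with a control who happened to read high. At follow-up each drifts back towards its own group's usual level, and the pair separates with no tracker effect. Adjusting the outcome model for the same reading does not cure this. The sign depends on who enrols: a higher-risk tracker group makes the tracker look harmful, and a better-controlled one makes it look helpful.

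The undated TIR raises a second, distinct issue. Taken before enrolment, TIR is a second reading of glycaemic level and reduces the bias. Taken after the tracker starts, it may itself be changed by the tracker, and matching on it would remove part of any real effect.

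A matched HbA1c or TIR difference would naturally be read as an effect of the tracker, because Section 6.2 describes the tracker as part of a behavioural intervention and Section 16.0 names better HbA1c as a possible benefit.

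**Working it through.** The plan gives no SD, effect size, alpha or sample-size derivation, so there is no figure of its own to reproduce. The check asks what difference would appear on HbA1c if the tracker had no effect.

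**From the documents:** 200 youth in the tracker group (Sections 1 and 8.0); HbA1c and TIR both in the score (Section 28.1).

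**Assumed, not in the documents:**
- D, the difference in usual HbA1c that remains after the other covariates are matched: 0 to 0.5 points
- between-person SD of usual HbA1c: 1.2 (variance 1.44)
- within-person SD: 0.7 (variance 0.49)
- TIR taken before the index date, with reliability 0.75 over 14 days and 0.85 over 90 days
- independent errors, 1:1 matching, 200 pairs, two-sided alpha 0.05

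**Formula.** False difference = (1 − R) × D, where R is the reliability of the matching information. With P the sum of 1/(error variance) over the readings used, 1 − R = (1/1.44) / (1/1.44 + P), and 1/1.44 = 0.694. A TIR reliability of 0.75 corresponds to an error variance of 1.44 × 0.25/0.75 = 0.48; a reliability of 0.85 corresponds to 1.44 × 0.15/0.85 = 0.254.

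**False difference at D = 0.5**

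| Matching information | P | 1 − R | False difference |
|---|---|---|---|
| One HbA1c, no TIR | 1/0.49 = 2.04 | 0.254 | 0.127 |
| One HbA1c + 14-day TIR | 2.04 + 1/0.48 = 4.12 | 0.144 | 0.072 |
| Mean of three HbA1c + 90-day TIR | 3/0.49 + 1/0.254 = 10.06 | 0.065 | 0.032 |

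The second row is closest to what Section 28.1 lists. The third approximates the fix.

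**False-positive rate.** The standard error is about √[2 × (0.49 + 1.44 × (1 − R))/200].
- One HbA1c + TIR: √[2 × 0.697/200] = 0.0835; 0.072/0.0835 = 0.86; rate about 14%.
- Three HbA1c + 90-day TIR: √[2 × 0.583/200] = 0.0764; 0.032/0.0764 = 0.42; rate about 7%.
- One HbA1c alone: √[2 × 0.856/200] = 0.0925; 0.127/0.0925 = 1.37; rate about 28%.

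Simulated propensity matching under the same assumptions agrees: about 0.12 points for one HbA1c alone, 0.07 points (13%) with TIR added, and 0.03 points (about 7%) with the fix.

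**Dependence on D (one HbA1c + TIR).** D = 0 gives 0.00 points, whatever the reliability. D = 0.2 gives 0.144 × 0.2 = 0.03 points and about 6% false positives. D = 0.5 gives 0.07 points and about 13%.

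**The case against.** The strongest reply is that the harm is conditional on facts that the documents do not give. There is no HbA1c or TIR level for either group, the control pool is not named, and with equal usual levels the bias is zero. Age, diabetes duration, insurance, race and device usage may also absorb part of any difference. All of this stands. What remains is that Sections 7.2 and 9.3 make a difference plausible, in either direction, and the plan offers no protection beyond two undefined readings.

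Four stronger readings are tempting but not supported:

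- **That baseline HbA1c is a single reading and TIR a 14-day one.** Section 28.1 gives no number, Section 26.0 speaks of levels in the plural, and the 14-day definition in Section 4.0 belongs to the endpoint. The supportable point is that both are unspecified.
- **That the false-positive rate is very high.** Matching on HbA1c alone with a usual-level difference of 1.0 point can push it above 80%. That calculation leaves out TIR, which Section 28.1 already lists and which nearly halves the bias if taken before enrolment.
- **That HbA1c and TIR are the declared outcomes of the matched comparison.** Section 28.1 names none. They are inferred from the endpoints in Section 4.0, and no objective in Section 2.0 is a tracker-versus-control contrast.
- **That no other analysis is planned.** The available text ends after Section 28.1, so silence there is weak evidence.

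It is also fair to say that the fix misses selection on a predicted 0.3-point rise. That is about trajectory rather than usual level; it could leave a difference even with a perfectly measured baseline, and it needs its own remedy.

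**Conclusion.** The point holds as a conditional weakness in the matching. Section 28.1 leaves the number of HbA1c readings and the dates of TIR open. If usual levels differ after matching, short readings may leave a false difference. Under the stated assumptions this is about 0 to 0.07 HbA1c points, with false positives up to about 13% instead of 5%. The size rests entirely on the assumed D, SDs and TIR reliability. No size was worked out for TIR as the outcome. The bias would be larger for meter users without TIR: 0.127 points at D = 0.5 if they have one HbA1c only. If TIR falls after the tracker starts, the comparison has the different fault of adjusting for a possible effect.

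This is a modest bias, and not one shown to be present. The change is still worth making: it uses data already collected in routine care, roughly halves the bias in the cases computed, and settles the dating of TIR.

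**What to change.** In Section 28.1:

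1. Define an index date for participants and for controls.
2. Replace baseline HbA1c with two covariates: the mean of the available measured HbA1c values in the 12 months before the index date, and the most recent of those values.
3. Replace time in range with TIR over up to 90 days of CGM, all before the index date, with a missing-TIR indicator for meter users.
4. Do not pool CGM-derived GMI with measured HbA1c.
5. Apply the same definitions to both groups and report balance on these covariates after matching.

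The 12-month and 90-day windows are judgements; the sponsor may choose others, provided they are fixed in advance and lie before the index date.

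**Cost.** A few sentences and some programming. Earlier HbA1c values should be in the medical record, and earlier CGM in the Diabetes Data Dock for linked patients.

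**Downside.** Youth with short histories contribute fewer values; Section 7.1 admits anyone more than 6 months from diagnosis. With one HbA1c plus 90-day TIR, P = 2.04 + 3.94 = 5.98, 1 − R = 0.104, and the false difference at D = 0.5 is 0.05 rather than 0.03 points.

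The change reduces the bias without removing it, and the predicted-rise recruitment route must be handled separately.
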